3. HUMAN SUBJECTS

3.1 SUBJECT POPULATION:

The gender and ethnic characteristics of the proposed subject population in this research protocol shall reflect the demographics of the population of Pittsburgh and the surrounding area. No exclusion criteria shall be based on race, ethnicity or gender. Because cystic fibrosis is largely a disease of Caucasians, our pool of potential subjects is >95% Caucasian reflecting the incidence of the disease across various ethnic and racial groups.

3.1.1 Inclusion of Women and Minority

Both men and women of all races and ethnic groups are eligible for this trial. Women who meet the inclusion criteria, and have none of the exclusion criteria, will be enrolled without restriction as dictated by the study protocols. Because of the use of a study medication, woman of child bearing potential must meet specialized inclusion/exclusion criteria to minimize this risk.

3.1.2 Inclusion of Children

Children under the age of 18 will not be recruited for this protocol because of the need to explore potential adverse effects of the study treatment more fully in adults.

3.2 INCLUSION CRITERIA:

Subjects 18 years or older with cystic fibrosis as documented by clinical features of CF, and documentation of a positive sweat test or two diseasing causing mutations in the CF gene, will be eligible..

3.3 EXCLUSION CRITERIA:

FEV₁<40%, use of supplemental oxygen or non-invasive ventilatory support, awaiting lung transplant, pregnancy or unwilling to comply with birth control during the intervention period, history of glucose-6-phosphate dehydrogenase (G6PD) deficiency or any contraindication to receiving methylene blue, hospitalization within the past 4 weeks prior to enrollment, need for additional antibiotics or steroids within the past 4 weeks prior to enrollment, change in maintenance CF therapies in the prior 4 weeks, inability to provide consent, baseline systemic hypotension (systolic BP<90mm Hg), chronic kidney disease (Cr >2.5 or requiring dialysis), severe anemia (Hgb <9 gm/dL in the last six months), history of portal hypertension or chronic liver disease, including hepatitis B and/or hepatitis C (with evidence of recent infection and/or active virus replication), defined as moderate to severe hepatic impairment (Child-Pugh Class B-C); history of abusing alcohol or illicit drugs within 28 days prior to study, severe pulmonary hypertension (mean PA pressure > 25), use of sildenafil or other pulmonary vasodilator, organ transplant of any kind, history of orthostatic hypotension or syncope, participation in another interventional trial in the previous 28 days.

4. RECRUITMENT AND INFORMED CONSENT PROCEDURES

4.1 RECRUITMENT METHODS:

Patients will be recruited from the CF Center at Children's Hospital of Pittsburgh and the University of Pittsburgh Medical Center. A list of eligible patients will be generated using a query of the Pittsburgh CF Center patient registry and patients who meet the lung function and bacterial pathogen criteria will be approached in clinic by one of the physicians or nurse coordinators to discuss the study and review the informed consent. A consent form will be given to the individual for review. The investigator and/or research coordinator will answer any questions and review study procedures and the potential risks and benefits of the study. The subject will be given a copy of the consent form to take home and read and may be called in approximately one week by the department research coordinator to answer questions and assess interest in participation. If the subject would like to enroll themselves, a visit will be arranged and written informed consent will be obtained by the investigator (pulmonologist) after any questions are answered and before any study procedures are performed. Patients meeting all inclusion/exclusion criteria and providing informed consent will be enrolled.

4.2 INFORMED CONSENT PROCEDURES:

Subjects will be recruited from the cystic fibrosis clinics at Children's Hospital of Pittsburgh and the Lung Center at Falk Clinic. Potential subjects will be identified by querying the CF Registry (IRB# 0405219). Patients must have given their consent for participation in the CF Registry to be included. The study will be introduced to eligible subjects by their primary pulmonologist or the research coordinator. The subject, if interested, will speak to the research coordinator. The subject will be given a copy of the consent form to take home and read and may be called in approximately one week by the department research coordinator to answer questions and assess interest in participation. If the subject is interested in participation, a visit will be arranged and written informed consent will be obtained by the investigator (pulmonologist) after any questions are answered and before any study procedures are performed.

The subject will be told research is voluntary and they are not obligated to participate if they are not interested. The subject will be presented with information on all studies they may qualify for prior to assessing for interest in a particular study.

If circumstances arise which necessitate that new information be provided to a subject, relevant subjects will be verbally notified by clinical staff as soon as possible. PI will be available to answer questions. Verbal notification will be documented in the subject's research chart. Upon approval of a revised consent, if applicable, all relevant subjects will be re-consented using the same process as outlined above as soon as possible.

5. Risks and Benefits

5.1 POTENTIAL RISKS

As with any experimental procedure, there may be adverse events or side effects that are currently unknown, and certain of these unknown risks could be permanent, severe or life threatening. Every attempt will be taken to minimize these risks.

5.1.1 *Risks of Sodium Nitrite Inhalation Solution:*

The first-in-man clinical study of nebulized sodium nitrite Inhalation Solution, Study AIR001-CS01, was a dose escalation study designed to identify the dose limiting toxicity, the maximum tolerated dose, and the pharmacokinetics of nebulized sodium nitrite administered. The most important safety finding was a decline in systolic and diastolic blood pressure at the highest dose tested, 176 mg. Dose-dependent asymptomatic increases in heart rate were noted at all doses, although at doses up to and including the maximum tolerated dose of 125 mg, the heart rate changes were well tolerated. Increase in heart rate was not always associated with a change in blood pressure. Significant levels of methemoglobin, or changes in pulmonary function, were not observed. Methemoglobin levels increased at the highest doses administered, but remained less than 3.5% in all subjects(12).

As with any drug product administered via inhalation, it is possible that susceptible individuals, such as those with unrecognized asthma, will develop bronchospasm upon exposure to inhaled sodium nitrite solution. There were no changes in pulmonary function noted in AIR001-CS01, which excluded subjects with asthma or abnormal baseline pulmonary function tests.

In Study AIR001-CS02, inhaled nitrite was generally well tolerated under hypoxic conditions at doses up to and including 113 mg. Additionally, a sustained reduction in hypoxia-induced pulmonary hypertension was demonstrated, suggesting that safely delivered doses of nebulized sodium nitrite result in clinically significant vasodilatation, presumably through a mechanism of intrapulmonary reduction of nitrite to NO. In this study, the significant treatment related adverse event was a decrease in blood pressure. The magnitude of the change in blood pressure from the hypoxic baseline was less than from the normoxic baseline, suggesting that hypoxia itself has an effect on BP.

The Hope Pharmaceuticals package insert includes the following warnings and precautions: hypotension, methemoglobin formation, risk for interaction with carbon monoxide (in the setting of smoke inhalation), use in the setting of known anemia (causing further decreased oxygen carrying capacity in the setting of methemoglobinemia), G6PD Deficiency, and use with PDE5 inhibitors and diuretics. Adverse reactions listed include syncope, hypotension, tachycardia, palpitations, dysrhythmia, methemoglobinemia, headache, dizziness, blurred vision, seizures, confusion, coma, nausea, vomiting, abdominal pain, tachypnea, dyspnea, anxiety, diaphoresis,

lightheadedness, injection site tingling, cyanosis, acidosis, fatigue, weakness, urticaria, generalized body numbness and tingling. Note that these reactions were reported with intravenous formulation of sodium nitrite being used to treat life-threatening cyanide poisoning, the total dose of nitrite given is 3-6 fold higher than in our study, and that the intravenous route may have more abrupt onset of effects. These adverse reactions are manifestations of systemic hypoperfusion or severe methemoglobinemia. The severe hypotension, methemoglobinemia, cardiac dysrhythmias and coma were reported in patients without life-threatening cyanide poisoning that were treated with intravenous doses less than twice those recommended for treatment of cyanide poisoning.

5.1.2 Risks of Blood Drawing:

The amount of blood to be drawn over the course of this research study could be a maximum of 5 tablespoons. To minimize the risks of blood tests, a licensed technician or registered nurse will draw blood. Common risks include temporary discomfort, bruising which may last for several days, redness, swelling, lower hemoglobin level. Infrequent risks include a subject may feel lightheaded or faint when blood is drawn. This is usually due to nervousness and is not usually serious. Rare risks include infection, and bleeding.

5.1.3 Risks of sputum induction

Sputum induction has been a standard study intervention in patients with CF for almost ten years and is generally well tolerated. Sputum induction may be associated with any of the following symptoms: You may experience: a salt water aftertaste, coughing, a need to swallow, sore throat, shortness of breath, wheeze, chest tightness, lightheadedness, nausea, and headache. Patients will be asked to report any symptoms during the procedure, and measures to assess symptoms will be taken as described in the Standard Operating Procedure for sputum induction (see Appendix).

5.1.4 Risks of withholding medications:

Participants will not be asked to withhold medications during the study.

5.1.5 Reproductive Risks:

It is not known if the study drug can affect an unborn baby. Therefore, subjects should not become pregnant or father a baby while on this study. If subjects are physically able to father a baby or become pregnant, subjects must use an effective method of birth control while on this study. If subjects become aware that they or their sexual partner is pregnant during the course of their participation in this research study, subjects must contact, as soon as possible, the study investigator.

5.1.6 Risks of Exhaled Nitric Oxide Measurement:

Exhaled Nitric Oxide Measurement is a non-invasive test commonly performed on asthma patients. There are no significant risks. Subjects may experience coughing during the test.

5.1.7 Risks of Spirometry:

Subjects may experience brief mild shortness of breath, wheezing, an increase in cough, or lightheadedness while doing spirometry.

5.1.8 Risks of Breach of Confidentiality:

Participation in this study also exposes subjects to risks associated with medical record review, specimen banking, and the completion of the CF respiratory symptom questionnaire. Some subjects may feel the questionnaire is too personal. To minimize this risk, privacy will be assured during completion of the questionnaire. Review of medical records and specimen banking are associated with the risk of loss of privacy or confidentiality. There is the possibility that if results of the medical record were generally known, the information may impact future insurability, employability, reproductive planning, or have a negative impact on family relationships. Note that the risk of breach of confidentiality exists during regular medical treatment. To minimize the risk of breach of confidential patient information we will do the following: All study visits are conducted in a private room. Samples will be bar coded as described above. Only IRB-approved staff will have access to any samples or information that is not de-identified. All research records will be kept in the locked office in the Pulmonary Medicine Allergy and Immunology office. Initials and identification number only will be used to identify patients. All databases are password protected.

5.2 PROTECTIONS AGAINST RISK

5.2.1 Protection Against Patient Risks Related to the Study Drug

The study has been designed with a focus on protecting subjects against risk from the medication including:

- Specific exclusion criteria to provide a stable population of subjects and non-enrollment of subjects with significant co-morbidities that might place them at excess risk (see exclusion criteria above).
- Continuous monitoring by the DSMB.
- Involvement by trained staff / investigators with experience in the administration of inhaled study medications.
- Specific holding criteria related to study adverse events.
- Frequent monitoring of vital signs and spirometry over the duration of the study.

5.2.2 Protection Against General Risks of Study Procedures

All research interventions/activities will be conducted in private patient care areas. The collection of sensitive information about subjects is limited to the amount necessary to achieve the aims of the research, so that no unneeded sensitive information is being collected.

All demographic and clinical information about the subject will be stored on an electronic password-guarded study database under the supervision of the investigator for this protocol. The electronic database has not been validated to be in full compliance with the FDA regulations at 21 CFR Part 11. Use of this electronic database is, however, felt to be acceptable due to the limited scope of this research study and the extent of data that will be collected. The data will be stored anonymously with a subject number. Information linking subject identifiers with the coded subject number will be stored under password protection on computers in locked areas, with access only to the database manager. Maintaining records in locked files in locked offices

will protect confidentiality of subjects. Access to the database will be limited to the data manager and staff under the supervision of the PIs.

To prevent excessive blood sampling, a single withdrawal of blood for a combination of clinically indicated and this research study will not exceed 5% of the circulating blood volume, and the cumulative withdrawal over 1 month will not exceed 10% of the circulating blood volume. In addition, careful attention will be made to cardiovascular status and hemoglobin evaluation.

Specimens will be stripped of subject identifiers and stored securely according to a similar coding protocol as described above. These specimens will be stored safely in the custody of the Principal Investigator responsible for the individual assays. These Investigators will limit future access to any remaining sample to only those investigators with prior IRB approval for their studies.

All staff involved in this study are properly credentialed and instructed in the areas of testing, confidentiality, and safety. To minimize the risks associated with the study procedures and/or collection of specimens, trained staff or experienced investigators will perform the study procedures.

5.3 ALTERNATIVE TREATMENTS

If subjects choose not to participate in this study, they are to continue their medical care under the direction of their primary physicians.

5.4 POTENTIAL BENEFITS

There will be no direct benefit to the subjects participating in this study, but the society at large may benefit from the increased knowledge gained from this study that will lead to new treatment for individuals diagnosed with cystic fibrosis in the future.

5.5 DATA SAFETY MONITORING PLAN

5.5.1 Data Safety Monitoring Board

A Data and Safety Monitoring Board (iDSMB) independent of the study investigators will monitor this clinical trial for additional measure of subject protection. The iDSMB consists of clinicians completely independent of the investigators who have no financial, scientific, or other conflict of interest with the trial. The iDSMB will conduct interim monitoring of accumulating data from research activities to assure the continue safety of human subjects, relevance and appropriateness of the study, and the integrity of research data.

5.5.2 Data Safety Monitoring Plan

Assuring patient safety is an essential component of this protocol. The study Principal Investigator has primary responsibility for the oversight of the data and safety monitoring. All adverse events experienced by subjects will be collected from beginning of visit 1 through final study visit. Study subjects will be routinely questioned about adverse events at study visits. The study investigators will evaluate all subject reported and observed AEs. All subjects who have AEs, whether considered associated with the use of the study medication or not, must be

monitored to determine the outcome. The clinical course of the AE will be followed up according to accepted standards of medical practice, even after the end of the period of observation, until a satisfactory explanation is found or the Principal Investigator considers it medically justifiable to terminate follow-up.

All untoward medical occurrences observed in subjects receiving the study drug will be recorded on the participants' adverse event worksheets by the study coordinator under the supervision of the principal investigator. AEs occurring pre-treatment, during active treatment and post-treatment will be summarized separately. The worksheets will then be reviewed for completeness and internal consistency. In addition to internal safeguards built into a computerized system, external safeguards will be put in place to ensure that access to the computerized system and to the data is restricted to authorized personnel. Training conducted by qualified individuals on a continuing basis will be provided to individuals in the specific operations with regard to computerized systems that they are to perform during the course of the study.

***Stopping Rule:**

Two distinct scenarios in which subjects must be removed from the study are anticipated.

First, the subject experiences a CF respiratory exacerbation marked by a persistent drop in FEV₁ >15% that is not temporally associated with nebulized sodium nitrite administration. The drop in FEV₁ would be seen on the first set of spirometry at a visit, prior to dosing of nebulized sodium nitrite for that day. In this case, subjects will be removed from the study and referred to their pulmonologist for treatment of the CF respiratory exacerbation.

- Drop in FEV₁ >15% on the first set of spirometry, prior to drug administration, on any study visit when compared with baseline spirometry collected at screening.

In the second scenario, nebulized sodium nitrite is associated with a dose-dependent intolerance that will be seen at the dose escalation visit 2, or after receiving the first dose of drug on visit 1. Specific intolerances of concern are acute bronchospasm, hypotension or methemoglobinemia. In this case, if any one of the below occurs at the 45 mg dose, subject will be removed from the study; if any occur at the 90 mg dose, the subject will return to the previously tolerated dose of 45 mg.

- Decrease in FEV₁ by >15% between measurements on an individual study visit.
- A decrease in systolic BP > 40 mmHg drop from pre-dose baseline or to <80mmHg and symptomatic
- SaO₂ drop below 88% and symptomatic or SaO₂ desaturation > 5% from baseline and symptomatic
- A single occurrence of venous methemoglobin level >5%
- Any serious adverse event thought to be possibly related to the study treatment

The Investigator will prepare a detailed written summary of serious, unexpected, and treatment related adverse events, and will compare, and contrast the event with prior events. The detailed written summary will be provided to the DSMB and the IRB.

In addition, the DSMB Report addressed the following information will be submitted to the IRB at the time of continuing review annually or more often as required:

- A list of the research personnel who participated in the data and safety monitoring.
- The frequency of monitoring that took place during the renewal intervals and/or the dates that data and safety monitoring was conducted.
- A summary of cumulative data related to unanticipated problems (including adverse events) including a determination of causality and whether the risk to benefit assessment has changed.
- If appropriate, a summary of pertinent scientific literature reports, therapeutic developments, or results of related studies that may have an impact on the safety of study participants or the ethics of the research study.
- A summary of the outcome of reviews conducted to ensure subject privacy and research data confidentiality.
- Final conclusions regarding changes to the anticipated benefit-to-risk assessment of the study participation and final recommendations related to continuing, changing, or terminating the study.
- We will comply with the reporting of adverse events to the IRB per the Human Research Protection Office Policies and Procedures Manual.

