Exclusion Criteria:	
1. Inability to provide consent2. Use of supplemental oxygen or non-invasive ventilatory support3. FEV₁ < 40%4. Awaiting lung transplantation5. Pregnancy or unwilling to comply with birth control during the intervention period6. History of glucose-6-phosphate dehydrogenase (G6PD) deficiency or any contraindication to receiving methylene blue7. Hospitalization within the past 4 weeks prior to enrollment8. Subject requires additional antibiotics or steroids within the past 4 weeks prior to enrollment9. Change in maintenance CF therapies in the past 4 weeks prior to enrollment10. Baseline systemic hypotension (systolic BP < 90 mm Hg)11. History of orthostatic hypotension or syncope12. Chronic kidney disease (creatinine > 2.5 or requiring dialysis)13. Severe anemia (Hgb <9 gm/dL in the last six months)14. History of portal hypertension or chronic liver disease, including hepatitis B and/or hepatitis C (with evidence of recent infection and/or active virus replication), defined as moderate to severe hepatic impairment (Child-Pugh Class B-C)15. History of abusing alcohol or illicit drugs within 28 days prior to study16. Severe pulmonary hypertension (mean PA pressure > 25)17. Use of sildenafil or other pulmonary vasodilator18. History of any organ transplantation19. Participation in another interventional trial in the previous 28 days
Study Endpoints:	
Primary endpoint:
 
The primary safety and efficacy endpoint is FEV₁. A sustained decrease in FEV₁ of >15% will be considered intolerable.
 
Secondary endpoints include exhaled NO (FE_{NO}), sputum nitrite concentration, quantitative bacterial cultures, percutaneous methemoglobin levels, blood pressure, and subject symptoms as measured by the CF Questionnaire-R.

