2.6 STOPPING RULES

Two distinct scenarios in which subjects must be removed from the study are anticipated.

First, the subject experiences a CF respiratory exacerbation marked by a persistent drop in FEV1 >15% that is not temporally associated with nebulized sodium nitrite administration. The drop in FEV1 would be seen on the first set of spirometry at a visit, prior to dosing of nebulized sodium nitrite for that day. In this case, subjects will be removed from the study and referred to their pulmonologist for treatment of the CF respiratory exacerbation.

Drop in FEV1 >15% on the first set of spirometry, prior to drug administration, on any study visit when compared with baseline spirometry collected at screening.

In the second scenario, nebulized sodium nitrite is associated with a dose-dependent intolerance that will be seen at the dose escalation visit 2, or after receiving the first dose of drug on visit 1. Specific intolerances of concern are acute bronchospasm, hypotension or methemoglobinemia. In this case, if any one of the below occurs at the 45 mg dose, subject will be removed from the study; if any occur at the 90 mg dose, the subject will return to the previously tolerated dose of 45 mg.

Specific criteria for dose-dependent intolerance are:

Decrease in FEV1 by >15% between measurements on an individual study visit.

A decrease in systolic BP > 40 mmHg drop from pre-dose baseline or to <80mmHg and symptomatic.

SaO₂ drop below 88% and symptomatic or SaO₂ desaturation > 5% from baseline and symptomatic

A single occurrence of venous methemoglobin level >5%

Any serious adverse event thought to be possibly related to the study treatment

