2.13 ENDPOINTS

2.13.1 Primary endpoint: The primary endpoint is FEV₁ to assess for bronchoconstriction induced by the study compound. We will compare FEV₁ before and at 30, and 120 minutes after dosing on day 0 with 45 mg dose, and day 7 with 90 mg dose. A sustained decrease in FEV₁ > 15% with the 45 mg dose will be considered intolerance and the study subject will be removed from the protocol. If a subject tolerates one week of the 45 mg dose but has a sustained decrease in FEV₁ after getting the first 90 mg dose, the subject will remain on the 45 mg dose for the duration of the study. If a subject experiences a CF respiratory exacerbation as defined by a drop in FEV₁ >15% on the first set of spirometry at any visit compared with baseline spirometry, then the subject will be removed from the study.

2.13.2 Secondary endpoints:

- FE_{NO} (exhaled NO)
- sputum nitrite concentrations
- CF Questionnaire-R subsection
- quantitative bacterial cultures for *P. aeruginosa* and/or *S. aureus*
- methemoglobin levels measured both non invasively and in whole blood
- systolic blood pressure

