2.14.2 WITHDRAWL CRITERIA

Study treatment will be discontinued in individual subjects during the day 0 inhalation if any of the following occurs regardless of symptoms:

- **Decrease in FEV₁ by >15%** between measurements on an individual study visit.
- A decrease in systolic BP > 40 mm Hg drop from pre-dose baseline or to <80mmHg and symptomatic;
- SaO₂ drop below 88% and symptomatic or SaO₂ desaturation > 5% from baseline and symptomatic
- A single occurrence of venous methemoglobin level >5%;
- Any serious adverse event thought to be possibly related to the study treatment

Any serious adverse event thought to be possibly related to the study treatment

If a study subject tolerates the 45 mg dose but develops hypotension, sustained > 15% decrease in FEV₁ (as measured at time points (30min and 120 min), or oxygen desaturation with the 90 mg dose on day 7, the subject will be observed. If after 4 hours of observation the subject's FEV₁ returns to baseline, the subject's SaO₂ is not greater than 5% drop from baseline, and the subject's systolic BP is not greater than 40 mm Hg drop from pre-dose baseline, the subject will be re-challenged with the 45mg dose; if the lower dose is tolerated, the subject will remain in the study at the lower dose.

Subjects will be withdrawn if at any time the investigator feels that it is not in the subject's best interest to continue.

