2.15 STATISTICAL ANALYSIS

2.15.1 Power Analysis and Sample Size:

The main adverse events reported in CF antibiotic trials are increased cough and change in respiratory symptoms. The overall subject driven discontinuation rate for these symptoms in both the placebo and treatment arms of recent antibiotics studies has ranged from 10-18%, although these symptoms do not necessarily correlate with bronchoconstriction (22, 23). Hypertonic saline is the most osmotically similar agent in use, and it causes 4.5% of children with severe CF lung disease to have an acute drop in FEV₁ of >15% (our stopping threshold) when used for sputum induction(24). Over a 4 week period, recent antibiotic studies have showed a decrease in FEV₁ of 3 to 6.5% in the placebo arms (19, 20, 22), so we are unlikely to have subjects reach the FEV₁ discontinuation threshold if nebulized sodium nitrite is safe but ineffective. Considering these data, we expect a 5-10% rate of discontinuation due to FEV₁ drop >15%, and we would consider up to 20% discontinuation acceptable. At a significance level of 0.05, a sample size of 33 is required to achieve 82% power to detect a difference of 0.14 using a one-sided binomial test, assuming that the population proportion under the null hypothesis is 0.06.

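### The dosing lists act on any FEV₁ fall of more than 15% within a visit, while the endpoint text requires a sustained fall for the same decision; one rule is needed

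*Combined protocol and SAP*

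**What the plan says.** **No persistence required.** Section 2.6 lists "Decrease in FEV1 by >15% between measurements on an individual study visit" among its criteria for dose-dependent intolerance, and the stopping rule in 5.5.2 repeats it: "Decrease in FEV₁ by >15% between measurements on an individual study visit". In both, the consequence is removal at 45 mg and return to 45 mg after a 90 mg dose. Section 2.14.2 puts the same FEV₁ line under the lead-in "Study treatment will be discontinued in individual subjects during the day 0 inhalation if any of the following occurs regardless of symptoms".

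**Persistence required.** The synopsis (Study Endpoints) states "A sustained decrease in FEV₁ of >15% will be considered intolerable". Section 2.13.1 says of day 0: "A sustained decrease in FEV₁ > 15% with the 45 mg dose will be considered intolerance and the study subject will be removed". For day 7 it keeps on 45 mg a subject who "has a sustained decrease in FEV₁ after getting the first 90 mg dose". The Day 7 paragraph of 2.14.2 refers to a "sustained > 15% decrease in FEV₁ (as measured at time points (30min and 120 min"; this is the only place where the word is tied to time points.

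**Other relevant text.** Sections 2.2.1 and 2.10 schedule spirometry before dosing and at 30 and 120 minutes on days 0 and 7. Table 1 (section 2.3) grades an FEV₁ decrease above 15% as moderate and above 25% as severe; its note 1 bars further dosing only after a severe, drug-related event. Section 2.15.1 cites a 4.5% rate, in children given hypertonic saline, of an "acute drop in FEV₁ of >15% (our stopping threshold) when used for sputum induction". The term sustained does not occur in that section.

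**The concern.** Two FEV₁ thresholds govern one decision, and no sentence says which prevails. This cannot be set aside as a safety rule on one side and an endpoint on the other, because 2.13.1 itself says who leaves the study at 45 mg and who stays on 45 mg. Section 2.14.2 contains both rules.

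Three things are at stake. First, the same subject can be handled differently depending on which section the site follows. Second, a subject can be withdrawn for FEV₁ under the lists and still count as tolerant under the primary endpoint definition. Third, the sustained wording leaves a gap for late bronchoconstriction, although acute bronchospasm is a named concern of the protocol.

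**Working it through.** **Inputs from section 2.15.1:** one-sided binomial test, α = 0.05, n = 33, null proportion 0.06, difference 0.14, so the alternative is 0.06 + 0.14 = 0.20. The documents give no rate for sustained falls.

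**1. The plan's own figure.** With X the number of events in 33, find the smallest r with P(X ≥ r | 0.06) ≤ 0.05.

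| r | P(X ≥ r given 0.06) |
|---|---|
| 3 | 0.318 |
| 4 | 0.134 |
| 5 | 0.045 |

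The cut-off is 5. Power is P(X ≥ 5 | 0.20) = 0.818, which reproduces the stated 82%.

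**2. Two illustrative subjects.**

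| | Pre-dose | 30 min | 120 min |
|---|---|---|---|
| A | 2.00 L | 1.66 L: (2.00 − 1.66)/2.00 = 17% fall | 1.84 L: (2.00 − 1.84)/2.00 = 8% fall |
| B | 2.00 L | 1.90 L: (2.00 − 1.90)/2.00 = 5% fall | 1.64 L: (2.00 − 1.64)/2.00 = 18% fall |

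Subject A after 45 mg: removed under 2.6, 5.5.2 and the day 0 list of 2.14.2; not intolerant under the synopsis or 2.13.1. After 90 mg: stepped down under 2.6 and 5.5.2; not under 2.13.1 or the Day 7 text of 2.14.2.

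Subject B: the lists act. The sustained rule cannot, because 120 minutes is the last scheduled reading unless the dose has already been judged not tolerated.

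**3. Effect on the count.** From the table in step 1, 4 events do not reject the 6% null and 5 do. One subject like A or B, counted or not, can move the result across that line.

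**4. How many subjects are affected.** Let f be the share of single falls that are present at both readings. Subjects classified differently on day 0 = 33 × (single-fall rate) × (1 − f). The values of f are assumptions.

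| f | Rate 6% | Rate 20% |
|---|---|---|
| 75% | 33 × 0.06 × 0.25 = 0.5 | 33 × 0.20 × 0.25 = 1.7 |
| 50% | 33 × 0.06 × 0.50 = 1.0 | 33 × 0.20 × 0.50 = 3.3 |
| 25% | 33 × 0.06 × 0.75 = 1.5 | 33 × 0.20 × 0.75 = 5.0 |

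**5. If the sustained rule were chosen instead.** If 0.06 and 0.20 are taken as single-fall rates, both must be multiplied by f and the cut-off found again at n = 33.

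| f | Null and alternative | Cut-off | Power |
|---|---|---|---|
| 75% | 4.5%, 15% | 5 | 56% |
| 50% | 3%, 10% | 4 | 42% |
| 25% | 1.5%, 5% | 3 | 23% |

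**6. False events from test error under the single-fall rule.** Assume no drug effect and three independent lognormal readings with log-scale SD s. The chance that either post-dose value is below 0.85 × pre-dose is 0.000127, 0.0039 and 0.0201 for s = 3%, 4% and 5%. Multiplied by 33, this is 0.004, 0.13 and 0.66 subjects.

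**The case against.** The strongest reply is that the rules are nested. Every sustained fall is also a single fall, 2.13.1 never says that a subject with a transient fall must continue, and 2.6 and 5.5.2 are mandatory. A site that applies the lists breaches no sentence elsewhere, and Subject B goes home with drug only if the site reads 2.13.1 alone. This stands: a reader might infer that the sections order incompatible actions, and they do not. What remains is that the endpoint text and the lists classify the same subject differently, and nothing tells the site or the analyst which to use.

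A reader might also infer that the sample size was planned on the single fall. Section 2.15.1 fits that rule better, since it equates an acute drop with the stopping threshold. But acute does not mean unsustained, 0.06 is never derived, and the section also weighs symptom-driven discontinuation and four-week FEV₁ decline. The documents do not prove the link.

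Third, the binomial test is named only in the power section. Section 2.15.2 describes tabulation, and the comparison in 2.13.1 is of FEV₁ before and after dosing. So the sensitivity of the test result is conditional on that test being used at the end.

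Finally, carrying the sustained wording into the lists would also be coherent. That is true, but it keeps the 120-minute gap and needs planning rates that the documents do not give.

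**Conclusion.** The inconsistency is real and sits in a decision threshold on the primary safety endpoint. It is a conflict of definitions; the sample-size arithmetic is correct for its inputs.

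Its size is modest. Under the assumed shares, about 0.5 to 1.5 subjects in 33 are classified differently on day 0 if the single-fall rate is 6%, and 1.7 to 5.0 if it is 20%. These figures rest on f between 25% and 75%, which the documents neither support nor contradict, and on treating every event as a day 0 fall. Conditional on the binomial test being the final analysis, one subject is enough to move p from 0.13 to 0.045.

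It would be tempting to say that the sustained rule destroys the power to detect an unsafe drug. That comparison would shrink the event while leaving the 6% null in place. With both rates rescaled, power is 56%, 42% or 23% under the assumed shares, and even this presumes that the planned rates refer to single falls.

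This should be corrected. It does not call the design or N into question.

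**What to change.** Use one rule in every section: **FEV₁ more than 15% below the pre-dose FEV₁ of that visit at 30 or 120 minutes.**

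- In 2.6, 5.5.2 and the day 0 list of 2.14.2, it replaces the current FEV₁ line, which does not name the reference reading.
- In the synopsis, 2.13.1 and the Day 7 text of 2.14.2, it replaces the sustained wording.
- Recovery decides only whether a subject is re-challenged at 45 mg after a failed 90 mg dose, as 2.2.1 and 2.14.2 already provide.
- Falls present at both readings are reported as a descriptive count.
- A sentence at Table 1 says that this rule governs dosing for FEV₁ falls of 15% to 25%, which the table grades as moderate.

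This rule is preferred because all three lists already act on a single fall, it covers a fall first seen at 120 minutes, and it fits the language of 2.15.1 better.

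Cost: wording only, with no new measurements; N = 33 and 82% power are unchanged. The downside is the set of subjects whose fall recovers by 120 minutes and who are then removed or stepped down: on day 0, the 0.5 to 1.5 (at a 6% rate) or 1.7 to 5.0 (at 20%) given above. There would also be some loss of 90 mg exposure on day 7, which cannot be quantified from the documents. Test error would add at most 0.7 false events in 33 over the SDs considered.

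If the team prefers the sustained rule, it should require the fall at both 30 and 120 minutes in all three lists, say how a fall first seen at 120 minutes is handled, and restate 0.06 and 0.20 in 2.15.1 as rates of sustained falls.
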